**Figure 2 Testing Procedure**  
Tezepelumab 210 Q4W vs Placebo

FEV1, forced expiratory volume in 1 second; LMK, Lund-Mackay score; NCS, nasal congestion score; NPSD, nasal polyp symptom diary; NPS, nasal polyp score; Q4W, every four weeks; SCS, systemic corticosteroids; SNOT-22, Sino-Nasal Outcome Test, 22 item; TSS, total nasal symptom score.

#### 4.1.3 Estimands

##### 4.1.3.1 Primary Estimand

- **Treatment:** Randomised treatment of tezepelumab 210 mg Q4W or placebo
- **Population of interest:** Adult participants with severe CRSwNP (total NPS  $\geq 5$ ) and an inadequate response to standard of care therapy, based on their randomised treatment and receiving at least one dose of IP
- **Endpoints of interest:** Change from baseline in co-primary endpoints: NPS and mean daily NCS at Week 52
- **Population level summary for the endpoint:** Difference in means between tezepelumab and placebo treatment groups
- **Handling of intercurrent events (ICEs):**
  - **Nasal polyp surgery:** The participants who had actual nasal polyp surgery would be considered poor outcome. The composite variable strategy will be applied where the worst possible score (ie. 8 for NPS and 3 for NCS) will be used for the post-surgery scores.
  - **SCS for NP:** The participants who received SCS (at least 3 consecutive days of OCS or equivalent 1 intramuscular injection for NP) would be considered poor outcome but less severe than surgery. The composite variable strategy will be applied where the

worst observation prior to the SCS will be carried forward (WOCF) for the post-SCS scores.

- **Treatment discontinuation:** The treatment policy strategy will be applied.
- **Adherence to background MFNS or an equivalent INCS and IP (including switching to other non-biologic/non-surgery/non-steroid treatments):** The treatment policy strategy will be applied. Data collected for participants who do not have rescue NP surgery or SCS are used regardless of the adherence of background MFNS or an equivalent INCS and IP and regardless of whether they switched to another non-biologic/non-surgery/non-steroid treatment.
- **Biologic use for NP:** The participants who received another biologic for NP would be considered poor outcome but less severe than surgery. The composite variable strategy will be applied where the worst observation prior to the biologic for NP will be carried forward (WOCF) for the post-biologic for NP scores.
- **Steroids and biologic use for comorbid conditions:** The treatment policy strategy will be applied for the participants who received another biologic for comorbid conditions.
- **COVID-19 related:** intercurrent events caused by COVID-19 include protocol deviations caused by COVID-19, COVID-19 vaccination, and COVID-19 infection. The treatment policy strategy will be applied.

#### 4.1.3.2 US FDA Primary Estimand

Following the US FDA Chronic Rhinosinusitis with Nasal Polyps: Developing Drugs for Treatment Guidance for Industry ([FDA 2023](#)), different strategies for the ICEs of SCS rescue for NP and biologic use for NP will be used than for primary estimand, i.e.:

- **SCS for NP:** The treatment policy strategy will be applied and data after SCS rescue will be included in the analysis.
- **Biologic use for NP:** The composite variable strategy will be applied where the worst possible score (i.e. 8 for NPS and 3 for NCS) will be used for the post-biologic scores.

#### 4.1.3.3 Supplementary Estimand

Composite variable strategy will be used for SCS for NP, biologic use for NP, and treatment discontinuation: the worst possible score will be used after the ICEs.

The key secondary and other secondary efficacy endpoints will use the same strategies for the intercurrent events unless noted otherwise.

## 4.2 Analysis Methods

### 4.2.1 Participant Disposition

Participant disposition will be summarised using the All participants analysis set. The number of enrolled participants will be summarised. The number and percentage of participants within each treatment group will be presented by the following categories; randomised, not randomised (and reason), received IP, did not receive IP (and reason), completed treatment, discontinued treatment (and reason), completed study (participants who completed IP and study, and participants who discontinued IP but completed study assessments), discontinued study (including reason), completed the short-term follow-up period, and completed the long-term follow-up period. Participant recruitment by country and centre will also be summarised.

The number and percentage of participants who discontinued IP, but remained in the study, will be presented by treatment group and option of follow up (Section 1.2).

Kaplan-Meier plots will be produced summarising the time (in days) to last dose of IP and premature withdrawal from the study separately. Participants without the premature event will be censored as described in Section 3.1.8.

The disposition due to the global/country situation will be summarized using the Randomised analysis set. The number and percentage of participants within each treatment group will be presented by the following categories: subjects who completed treatment, subjects who discontinued treatment due to the global/country situation, subjects who completed the study, and subjects who withdrew from the study due to the global/country situation. The global/country situation study disruptions will also be summarized for the Randomised analysis set. The number and percentage of participants within each treatment group will be presented by the following categories: participants with at least one disruption due to global/country situation (including type of disruption), and participants who discontinued treatment or withdrew from study due to global/country situation.

### 4.2.2 Demography and Other Baseline Characteristics

All demographic data and baseline characteristics will be summarised by treatment group and total for the FAS.

- Demographic data (eg, age, age group, gender, ethnicity, and race)
- Stratification factors from the IWRS and eCRF
- Subgroups defined in Section 3.1.6
- Other baseline characteristics defined in Section 3.1.7

- Important PDs

The number of participants in each of the analysis sets defined in Section 2.1 will be summarised.

Disease characteristics collected on the Respiratory Disease History, Nasal Polyposis Respiratory Disease History, and Nasal Polyposis Surgery eCRFs will also be summarised. The time since diagnosis, age at diagnosis, and time since last surgery will be calculated and summarised.

#### **4.2.3 Medical and Surgical History**

Medical and surgical histories will be summarised by MedDRA Preferred Term (PT) within the System Organ Class (SOC) level of MedDRA.

#### **4.2.4 Prior and Concomitant Medications**

The number and percentage of participants receiving each medication (by ATC code and generic name) will be presented by treatment group and total for the FAS. Separate tables will be presented for all medications received during each of the following periods as defined in Section 3.1.3: Prior, Concomitant (on-treatment), and Concomitant (post-treatment).

A separate table for prior biologics taken for asthma and/or NP, either marketed or in a clinical study, will be presented by treatment group and total for the FAS.

A table for standard of care medications at study entry will be produced displaying any standard of care medication for chronic rhinosinusitis with nasal polyps stable for at least 30 days prior to V1.

A separate table will be presented for participants who took disallowed concomitant medications. Disallowed medications will include medications defined as prohibited according to Section 6.4 of the CSP. They will be defined following a physician review (prior to primary database lock) of the unique combinations of ATC code and generic terms captured and are important protocol deviations.

Medications will be classified using WHO Drug Dictionary Mar 2024.

#### **4.2.5 Exposure and Compliance**

Exposure and treatment compliance derivation details are defined in Section 3.6.1.

Extent of exposure to IP, and total number of dosing occasions will be summarised by treatment group, for the Safety Set. Additionally, cumulative extent of exposure will be summarised for the Safety Set:

- any participant exposed,  $\geq 4$ ,  $\geq 8$ ,  $\geq 12$ ,  $\geq 16$ , etc., and  $\geq 52$  weeks,
- $>0$  -  $< 4$ ,  $\geq 4$  -  $< 8$ ,  $\geq 8$  -  $< 12$ , etc.  $\geq 48$  -  $< 52$ , and  $\geq 52$  weeks.

The date and time of IP administrations will be listed using the Safety Set.

Compliance with taking the regularly scheduled MFNS or equivalent INCS medication as recorded in the daily diary will be summarised bi-weekly by treatment group. The compliance with IP (%) and the number and percentage of subjects in each study treatment compliance (%) category (<80, 80-100, >100) will also be summarized. Compliance with the use of the daily diary will also be summarised bi-weekly by treatment group. Compliance with MFNS/INCS, IP and daily diary will be presented for Full Analysis Set.

#### 4.2.6 Co-Primary Endpoints

##### 4.2.6.1 Primary Estimand Analysis

For the primary estimand the primary analysis of the co-primary efficacy endpoints (mean change from baseline in NPS at 52 weeks and mean change from baseline in NCS at 52 weeks) uses a composite variable strategy in which data collected after nasal polyp surgery will be replaced with the worst possible score (WPS). Data collected after SCS for NP will be replaced with the worst post-baseline observation prior to the SCS for NP (WOCF). Data collected after treatment discontinuation without surgery or SCS for NP will be included in the analysis. For participants whose post-baseline data are all missing, the baseline value will be used in the place of WOCF. For participants who discontinue the study without NP surgery or SCS/biologic for NP, a multiple imputation (MI) approach will be used to impute missing Week 52 value assuming missing at random (MAR). A random seed of 539612 will be used for both monotone and non-monotone imputations.

Of note, biologics are prohibited medications per the CSP Section 6.4. However, if biologics are used for NP, the same strategy used for the SCS for NP will be applied.

The following steps will be taken to generate completed datasets up to Week 52 for analysis:

**Step 1:** Data collected after date of surgery, SCS for NP, or biologic for NP treatment will be set to missing for the purpose of imputation. For the NCS, if the intercurrent event occurred prior to the last day of a bi-weekly interval, the bi-weekly mean NCS for that period and all periods afterwards will be set to missing.

**Step 2:** Based on the dataset from Step 1, the intermittent missing data will be imputed using the MCMC method in SAS PROC MI with an IMPUTE=MONOTONE statement for each treatment group separately. The imputation model will include baseline co-morbid asthma/AERD/NSAID-ERD status, prior surgery status, region, baseline value, and data at each timepoint. 100 imputed datasets will be generated.

**Step 3:** The remaining monotone missing data will be imputed using the MI procedure with the ‘MONOTONE REG’ option for each treatment group separately. The imputation model will include baseline co-morbid asthma/AERD/NSAID-ERD status, prior surgery status, region, baseline value, and data at each timepoint.

**Step 4:** In the datasets from Step 3, replace post-surgery score with WPS, and replace post-SCS/biologic for NP score with WOCF. If a participant received both NP surgery and SCS for NP/biologic for NP, scores post-surgery will be set to WPS.

Each of the imputed datasets at Week 52 will be analysed using the analysis of covariance (ANCOVA) model with treatment group, baseline co-morbid asthma/AERD/NSAID-ERD status, prior surgery status, and region as factors (based on eCRF), and the baseline value as a covariate. Rubin’s rule will be applied to combine analysis results (point estimates and standard errors) from the imputed datasets using PROC MIANALYZE.

Descriptive statistics including number of participants, mean, standard error, and least squares (LS) means will be provided at Week 52. In addition, difference in LS means (using the observed marginal distribution of the sample covariates) and the corresponding 95% confidence intervals (CIs) will be provided along with the p-value. A single asterisk (\*) will be used to denote a result that is statistically significant at alpha = 0.05 and a double asterisk (\*\*) will be used to denote a result that is statistically significant at alpha = 0.01. Nominal p-values will be presented unless specified otherwise.

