9.4.1.1 Primary Estimand

The primary estimand is described as follows:

- **Treatment:** Randomised treatment of tezepelumab 210 mg Q4W or placebo
- **Population of interest:** Adult participants with severe CRSwNP (total NPS ≥ 5) and an inadequate response to standard of care therapy, based on their randomised treatment and receiving at least one dose of IP
- **Endpoints of interest:** Change from baseline in co-primary endpoints: NPS and bi-weekly mean NCS at Week 52.
- **Population level summary for the endpoint:** Difference in means between tezepelumab and placebo treatment groups
- **Handling of intercurrent events (ICEs):**
 - **Nasal polyp surgery:** The participants who had nasal polyp surgery during the study conduct would be considered poor outcome. The composite variable strategy will be applied where the worst possible score (ie, 8 for NPS and 3 for NCS) will be used for the post-surgery scores.
 - **SCS for NP:** The participants who received SCS (at least 3 consecutive days of OCS or equivalent 1 intramuscular injection) for NP would be considered poor outcome but less severe than surgery. The composite variable strategy will be applied where the worst observation prior to the SCS will be carried forward (WOCF) for the post-SCS scores.
 - **Treatment discontinuation:** The treatment policy strategy will be applied. Data collected for participants who do not have rescue therapy are used regardless of whether treatment discontinuation occurs.
 - **Adherence to background MFNS or an equivalent INCS and IP:** The treatment policy strategy will be applied. Data collected for participants who do not have rescue NP surgery or SCS are used regardless of the adherence of background MFNS or an equivalent INCS and IP.
 - **Biologic use for NP:** The participants who received another biologic for NP would be considered poor outcome but less severe than surgery. The composite variable strategy will be applied where the worst observation prior to the biologic for NP will be carried forward (WOCF) for the post-biologic scores.
 - **Steroids or biologic use for co-morbid conditions:** The treatment policy strategy will be applied for the participants who received steroids or another biologic for co-morbid conditions.
 - **COVID-19 related:** intercurrent events caused by COVID-19 including protocol deviations caused by COVID-19, COVID vaccination, and COVID-19 infection. The treatment policy strategy will be applied.

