9.4.2 Efficacy

9.4.2.1 Primary Endpoint(s)

For the primary estimand, data collected after surgery will be replaced with the worst possible score. Data collected after SCS will be replaced with the worst observation prior to the SCS (WOCF). Data collected after treatment discontinuation without surgery or SCS will be included in the analysis. For participants whose post-baseline data are all missing, the baseline value will be used in the analysis. For participants who discontinue the study without surgery or SCS, multiple imputation will be used to impute missing data assuming missing at random (MAR).

Each of the imputed datasets will be analysed using an analysis of covariance (ANCOVA) model with the baseline value as a covariate, and treatment group, baseline co-morbid asthma/AERD/NSAID-ERD status, prior surgery status, and regions as factors. Rubin's rule will be applied to combine analysis results (point estimates and standard errors) from the imputed datasets. Descriptive statistics including number of participants, mean, standard error, and least squares (LS) means will be provided for each time point. In addition, difference in LS means and the corresponding 95% confidence intervals (CIs) will be provided along with the p-values.

For the FDA and supplementary estimands, strategies for the ICEs are described in Sections [9.4.1.2](#) and [9.4.1.3](#) and will be applied accordingly. Additional sensitivity analyses will be performed to examine the MAR assumptions about missing data. Details of the supplementary and sensitivity analyses will be included in the SAP.

Subgroup analyses

For the purpose of exploring consistency of treatment effect across subgroups, a similar model will be fitted as for the primary analysis with additional factors for the relevant subgroup variable and its interaction with treatment. Key subgroups include:

- Age
- Gender
- Race
- Prior surgery status
- Allergic rhinitis
- Co-morbid asthma status
- AERD/NSAID-ERD
- Baseline eosinophil count
- Body mass index
- Region

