## 1 STUDY DETAILS

This is the statistical analysis plan (SAP) for study D5242C00001. The SAP describes the statistical analyses specified in the latest version of the clinical study protocol (CSP) in more detail. Any changes to what is specified in the CSP will be described.

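### After SCS or biologic rescue, SAP 4.2.6.1 carries forward the worst post-baseline score, whereas the protocol and the SAP's own estimand say the worst observation before rescue; the narrowing is not declared

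*SAP*

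**What the plan says.** Three places give the rule without excluding baseline.

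- Protocol 9.4.1.1 treats SCS for nasal polyps as a poor outcome, less severe than surgery, "where the worst observation prior to the SCS will be carried forward (WOCF) for the post-SCS scores". It says the same for a biologic.
- Protocol 9.4.2.1: "Data collected after SCS will be replaced with the worst observation prior to the SCS (WOCF". It adds that baseline is used when every post-baseline value is missing.
- SAP 4.1.3.1 repeats the estimand: "worst observation prior to the SCS will be carried forward (WOCF) for the post-SCS".

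SAP 4.2.6.1, which the programmer will follow, is narrower: "Data collected after SCS for NP will be replaced with the worst post-baseline observation prior to the SCS for NP (WOCF". It extends this to biologics ("if biologics are used for NP, the same strategy used for the SCS for NP will be applied") and brings baseline in only as a fallback: "For participants whose post-baseline data are all missing, the baseline value will be used in the place of WOCF". Step 4 writes the resulting value into every imputed dataset before the ANCOVA. SAP 4.2.9.1 Step V does the same for the analysis to Week 76.

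SAP Section 1 promises: "Any changes to what is specified in the CSP will be described". Section 6 lists only added exploratory analyses and does not mention this rule.

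**The concern.** If baseline counts as an observation before rescue, a rescued participant's change from baseline cannot be negative. If only post-baseline values count, it can be. A participant whom the estimand classes as a poor outcome may then enter the co-primary ANCOVA as improved.

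The rule governs NPS and NCS under the primary estimand. By cross-reference it also governs loss of smell, SNOT-22, LMK and NPSD TSS. Two programmers, one working from the protocol and one from SAP 4.2.6.1, could derive different Week 52 values for the same person.

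The responder analyses carry a related conflict. SAP 4.2.7.2.1, 4.2.8.7 and 4.2.9.7 define anyone with SCS, biologic or surgery at or before the time point as a non-responder. The treatment comparison, however, dichotomises the values produced by Steps 1 to 4. Under the post-baseline rule, those values can show a response in a rescued participant.

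**Working it through.** **Planned power (Protocol 9.2).** Inputs: 200 per arm, two-sided 1%; NPS effect -1.8, SD 2.25; NCS effect -0.87, SD 1.22. The standard error is SD × √(2/200), which is 0.225 for NPS and 0.122 for NCS. Then z = 1.8/0.225 = 8.00 and 0.87/0.122 = 7.13. The lower bound on joint power (sum of the two powers minus 1) is above 99.99%, consistent with the stated minimum of 95%.

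**Scoring.** Let b be baseline and w the worst post-baseline value before rescue.

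- SAP 4.2.6.1: change = w − b.
- Literal estimand wording: change = max(b, w) − b.

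For b = 6 and w = 4, these give -2 and 0. Over baseline NPS 5 to 8 (the entry floor is 5) and w from 0 to 8, 26 of 36 combinations are negative under the first rule and 0 of 36 under the second. This counts possible combinations, not their frequency. The rules differ only when w < b, that is, when every pre-rescue post-baseline score was better than baseline.

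**Responders.** The case b = 6, w = 4 meets both the 1-point and the 2-point NPS criteria once dichotomised. A rescued participant whose worst post-baseline SNOT-22 was at least 8.9 below baseline likewise becomes a responder. With baseline counted, the change is at least 0 and neither happens.

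**Reach.** Protocol 9.2 plans a 35% placebo rate for SCS and/or surgery decision and 11% for surgery decision, each with HR 0.33. The tezepelumab rates are 1 − 0.65^0.33 = 13.3% and 1 − 0.89^0.33 = 3.8%. Post-surgery scores take the worst possible value, so surgery cases fall outside this rule. Removing the surgery-decision rate gives lower figures of 35% − 11% = 24% on placebo and 9.5% on tezepelumab; removing nothing gives 35% and 13.3%. That is about 48 to 70 placebo and 19 to 27 tezepelumab participants.

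**Shift in the treatment difference.** Let d be the mean of max(b − w, 0) among rescued participants. Counting baseline raises each arm mean by p × d, so the difference moves by p_tez × d_tez − p_pbo × d_pbo. The documents do not give d, so the values below are assumptions. For NPS:

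| d placebo | d tezepelumab | Shift, lower rates | Shift, upper rates |
|---|---|---|---|
| 0.25 | 0.25 | -0.036 | -0.054 |
| 0.5 | 0.5 | -0.073 | -0.109 |
| 1.0 | 1.0 | -0.145 | -0.217 |
| 0.25 | 1.0 | +0.035 | +0.045 |
| 0.5 | 1.5 | +0.022 | +0.024 |
| 0.5 | 2.0 | +0.070 | +0.090 |

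A negative shift means the SAP wording understates the effect. The sign turns at d_tez/d_pbo = p_pbo/p_tez, which is 0.24/0.0948 = 2.53 or 0.35/0.1325 = 2.64.

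For NCS, equal d of 0.1 to 0.5 gives -0.015 to -0.109. The unequal pairs tried (placebo 0.1 with tezepelumab 0.5, and 0.2 with 0.8) give +0.023 to +0.036.

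**Power after the shift.** Applied to the planned effects, the NPS difference lies between -2.02 and -1.71 and the NCS difference between -0.98 and -0.83. Power at 1% stays above 99.99% for each.

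**The case against.** The strongest reply is that the SAP merely makes the protocol operational. Protocol 9.4.2.1 falls back to baseline when all post-baseline data are missing, which rescued participants would not need if baseline always counted. Protocol 9.4 also calls its section a summary and leaves detail to the SAP. This stands in part. A reader might infer an outright contradiction, but the documents show an unqualified phrase that was later narrowed, and a post-baseline reading of the protocol is tenable. The fallback does not settle it, because the protocol sentence is not confined to rescued participants and the estimand wording remains unqualified in both documents.

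Second, the protocol (Schedule of Activities footnote u and Section 8.1.4) asks for an endoscopy before SCS, and SAP 3.1.4 includes unscheduled data in maximum values. The worsening that prompted rescue will therefore often be captured for NPS, and both rules then give the same score. That stands, and it makes the affected cases fewer. It helps NCS less, because Step 1 sets to missing the bi-weekly mean of any interval in which rescue occurs before its last day.

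Third, the US FDA estimand uses treatment policy for SCS and the worst possible score for biologics, and the supplementary estimand uses the worst possible score for both. For NPS and NCS neither uses WOCF, so neither is affected. They answer other questions, however, and do not say which rule defines the primary estimand.

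**Conclusion.** The inconsistency is real and sits in the scoring rule for the primary estimand of both co-primary endpoints. Its numerical effect is small: -0.22 to +0.09 on the NPS difference over the assumptions tried, with power and the likely conclusion unchanged. This rests on the plan's rescue rates, of which the 35% includes surgery decisions, and on assumed values of d.

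Three stronger readings are not supported.

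- A reader might infer that the rule favours the drug. With more rescue planned on placebo, it works against the drug unless d on tezepelumab is about 2.5 times d on placebo or more.
- A reader might infer that every participant who improved before rescue is scored differently. Someone who improved and then returned to baseline or worse before rescue scores the same under both rules.
- A reader might set an individual change of -2 beside the planned effect of -1.8. The first is one person's change and the second a difference between arms, so the comparison says nothing about size.

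The responder conflict follows from the SAP's own text and does not depend on how the protocol is read.

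**What to change.** Before unblinding at primary database lock, use one WOCF definition in SAP 4.1.3.1, 4.2.6.1 (text and Step 4) and 4.2.9.1 Step V. The preferable choice is the worst of baseline and all observations before the SCS or biologic. It matches the literal estimand wording and removes the responder conflict for these rescues.

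If the post-baseline rule is intended, reword the estimand, list the change in SAP Section 6, and run the baseline-inclusive version as a sensitivity analysis. Also set rescued participants to non-responder in the imputed comparisons of 4.2.7.2.1, 4.2.8.7 and 4.2.9.7.

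The cost is a few sentences of SAP text, a small programming change and at most one extra analysis run. Counting baseline makes the arm means slightly less favourable: over the d values in the table, by 0.06 (0.24 × 0.25) to 0.35 (0.35 × 1.0) NPS points on placebo and 0.02 (0.095 × 0.25) to 0.27 (0.1325 × 2.0) on tezepelumab. Leaving the choice until after unblinding would make it data-dependent.
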